6.5.2 Laboratory Tests

Descriptive summaries of laboratory values and changes from Day 1 and throughout the study will be generated. The proportion of patients who experience treatment-emergent laboratory abnormalities will be compared between groups.

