Appendix 1 Schedule of Assessments: Table A (cont.)

	Group A (A1 and A2)												
	Screening ¹	Immunization Study Period						OOE ^{2,3}			WD from Treatment	Unscheduled ⁴	Delayed Dosing ⁵
Study Day (unless noted) (Window)	-28 to -1	1 (BL)¹	15 (±2 d)	85 (±4 d)	112 (±4 d)	140 (±4 d)	169²	169²	q22w (±4 d) (-2 w prior to q24 w)	q24 w³ (±2 w)			
Week	-4 to -1	1	2	12	16	20	24	24	q22 w³	q24 w³			
CD4 count ²⁰	x	x				x			x	x	x		
IgG subtype		x		x					x		x		
Total Ig, IgA, IgG, IgM	x	x		x			x	x	x		x		
Flow cytometry ²¹		x	x	x	x	x	x	x	x	x	x		
Routine safety labs ²²	x	x	x	x	x	x	x	x	x	x	x	x	
Pretreatment with IV methylprednisolone and an antihistamine ²³		x	x					x		x			x
IV OCR ²⁴		x	x					x		x			x
Influenza vaccine ²⁵				I/M ²⁵ → Influenza → post-vaccine assessment after 4 weeks									
KLH				I/M ²⁶	I/M ²⁶	I/M ²⁶	M	M ²⁶					

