Appendix 1 Schedule of Assessments: Table B (cont.)

		Group B												
	Screening ¹	Immunization Study Period				OOE ^{2,3}						WD from Treatment ⁴	Unscheduled ⁴	Delayed Dosing ⁵
Study Day (Unless Noted) Window	-28 to -1	1	28 (±4 d)	56 (±4 d)	84¹ (±4 d)	84¹ (±4 d)	98 (±2 d)	238 (±4 d)	252 (±2 d)	q22w (±4 d) (-2 w prior to q24 w)	q24 w³ (±2 w)			
Week	-4 to -1	—	4	8	12	12	14	34	36	q22 w³	q24 w³			
HBV DNA ¹⁹ monitoring		X			X	X		X	X	X		X		
RPR	X													
CD4 count ²⁰	X					X		X	X	X	X	X		
IgG subtype		X ²¹			X ²¹	X ²¹		X		X		X		
Total Ig, IgA, IgG, IgM	X	X	X	X	X	X		X		X		X		
Flow cytometry ²²		X			X	X	X	X	X	X	X	X		
Routine safety labs ²³	X	X	X	X	X	X	X	X	X	X	X	X	X	X
Pretreatment with IV methylprednisolone and an antihistamine ²⁴						X	X		X		X			X
IV OCR ²⁵						X	X		X		X			X

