4.5 IMMUNOPHENOTYPING ANALYSES

For immunophenotyping analyses, data will be presented for Groups A1 and A2 separately as well as for Group A (Groups A1 and A2 combined) and Group B.

Summaries will be presented separately within the following study periods:

- ISP
- SFU Period after the ISP (these patients did not enter the OOE)
- OOE
- SFU Period after completing the OOE

The humoral and cellular immunity outcome measures in this study are as follows:

- Flow cytometry, which will include (but is not limited to) the following cells:
 - Total B cells (CD19+)
 - B-cell subsets (e.g., memory B cells, naïve B cells, and plasma cells)
 - Total T cells (CD3+)
 - T helper cells (CD3+ and CD4+)
 - Cytotoxic lymphocyte T (CD3+ and CD8+)
 - Natural killer cells (CD3– and CD16/56+)
- Quantitative Ig:lg levels (including total Ig, IgG, IgG subtypes, IgM, and IgA)

Ocrelizumab—F. Hoffmann-La Roche Ltd
22/Statistical Analysis Plan BN29739

For each flow cytometry parameters, the absolute values and change from baseline (Day 1) will be summarized over time by treatment group. Summary statistics calculated will include mean, median, SD, minimum, and maximum. For CD19 cells, the number and percentage of patients whose CD19 counts have repleted will be presented at each timepoint. Repletion is defined as the CD19-cell count having returned to their baseline value (Day 1) or lower limit of normal (≥ 80 cells/ μL), whichever is lowest. The median CD19-cell count will be displayed graphically over time from the start of study treatment.

For immunoglobulin levels (IgG, IgM, and total Ig), the absolute values and change from baseline will be summarized over time by treatment group. Summary statistics calculated will include mean, median, SD, minimum, and maximum. At each timepoint, the number and percentage of patients with immunoglobulin levels lower than the lower limit of normal will be presented. For each immunoglobulin, the number and percentage of patients with single and replicated laboratory abnormalities will be summarized by treatment group. The mean immunoglobulin levels (IgG, IgM, and total Ig) will be displayed graphically over time from the start of study treatment.

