4.6.4 Laboratory Data

4.6.4.1 General Laboratory Evaluation

The summaries described below for general laboratory assessments will be produced for both the ISP and for the OOE separately.

For each laboratory test, absolute and changes from baseline values at each visit will be summarized by treatment group. Summary statistics calculated will include mean, median, SD, minimum, and maximum. The baseline value will be the last value prior to the first dose of ocrelizumab for patients in Group A and prior to the first immunization for patients in Group B. When laboratory data are presented over time, the laboratory values will be time-windowed into a common visit structure. If multiple values of the same laboratory parameter occur within the same time window, the worst value (i.e., the

value furthest away from the midpoint of the normal range) will be included in calculations of summary statistics.

For each laboratory test, the number and percentage of patients with single and replicated laboratory abnormalities will be summarized by treatment group.

In addition, for liver laboratory parameters, the number and percentage of patients with an elevated postbaseline AST or ALT levels will be summarized by treatment group.

During the SFU Period after either the ISP or the OOE, for each laboratory test, absolute and changes from baseline values at each visit will be summarized by treatment group. Summary statistics calculated will include mean, median, SD, minimum, and maximum. These summaries will only be presented if there is a sufficient volume of patient data available to allow meaningful interpretation.

Section 6.5.2 of the protocol states that for each laboratory test, individual patient values will be listed, and values outside the standard reference range will be flagged. To maintain consistency with the other Phase 3 studies in the ocrelizumab program, this data listing will not be prepared. The summary tables described above are considered adequate to describe general laboratory abnormalities, without the need for this data listing.

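### Routine-lab abnormality percentages are compared per patient over five post-baseline draws in Group A and three in Group B, which raises the Group A figure even with no drug effect

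*SAP*

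**What the plan says.** SAP 4.6.4.1 (General Laboratory Evaluation) produces its laboratory summaries once for the ISP and once for the optional extension. Within each period, "For each laboratory test, the number and percentage of patients with single and replicated laboratory abnormalities will be summarized by treatment group". It adds the percentage of patients with an elevated post-baseline AST or ALT. Per-visit output consists of means, medians, SDs and ranges of values and changes; no abnormality percentage is given by visit. The same section drops a flagged patient-level listing because the summary tables are thought sufficient.

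Protocol 6.5.2 makes the comparison explicit: "The proportion of patients who experience treatment-emergent laboratory abnormalities will be compared between groups".

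SAP 4.5 (Immunophenotyping Analyses) uses the same measure for immunoglobulins: "For each immunoglobulin, the number and percentage of patients with single and replicated laboratory abnormalities will be summarized by treatment group". It also presents, at each timepoint, the share of patients below the lower limit of normal (LLN).

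Neither document defines *single* or *replicated*, and neither adjusts these percentages for the number of draws or for the length of the ISP, which is 24 weeks in Group A and 12 weeks in Group B.

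**The concern.** A percentage of patients with any abnormal result depends on how often each patient is tested. The two groups are not tested equally often in the ISP, so the percentages can differ when ocrelizumab does nothing to the laboratory values.

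For routine safety labs Group A has more draws, so its at-least-one percentage is pushed up. A reader of the table would see an apparent excess of laboratory abnormalities on ocrelizumab, and could not tell how much of it comes from the schedule. No by-visit abnormality rate or flagged listing is planned against which to check it. The AST/ALT percentage has the same weakness.

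**Working it through.** The documents give no figure on this point, so there is none to reproduce.

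**Draw counts.** From the ISP columns of Appendix 1, Tables A and B. Day 1 is excluded because SAP 4.6.4.1 takes baseline as the last value before the first ocrelizumab dose (A) or the first immunization (B).

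| Test | Group A days | Group B days | Draws, A v B |
|---|---|---|---|
| Routine safety labs | 15, 85, 112, 140, 169 | 28, 56, 84 | 5 v 3 |
| Total Ig, IgA, IgG, IgM | 85, 169 | 28, 56, 84 | 2 v 3 |
| IgG subtypes | 85 | 84 | 1 v 1 |

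**Assumptions, not in the documents.** The chance p that one draw is abnormal is the same in both groups (2%, 5% or 10%). The within-patient correlation ρ runs from 0 to 0.9.

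**Formulas.** Independent draws: P(at least one of n) = 1 − (1 − p)^n. Correlated draws use a beta-binomial with a + b = (1 − ρ)/ρ and b = (1 − p)(a + b). Then P(none of n) is the product of (b + i)/(a + b + i) for i = 0 to n − 1.

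**Routine labs, p = 5%.**
- ρ = 0: 1 − 0.95^5 = 22.6% in A; 1 − 0.95^3 = 14.3% in B.
- ρ = 0.6: a + b = 0.667 and b = 0.633. The factors are 0.95, 0.98, 0.9875, 0.9909 and 0.9929. The first three multiply to 0.919, giving 8.1% in B; all five multiply to 0.9045, giving 9.6% in A.

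| ρ | At least one, A v B | At least two, A v B | Exactly one, A v B |
|---|---|---|---|
| 0 | 22.6% v 14.3% | 2.26% v 0.73% | 20.4% v 13.5% |
| 0.3 | 14.4% v 10.8% | 6.32% v 3.39% | 8.0% v 7.4% |
| 0.6 | 9.6% v 8.1% | 6.30% v 4.57% | 3.3% v 3.5% |
| 0.9 | 6.0% v 5.7% | 5.38% v 4.98% | 0.6% v 0.7% |

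With independent draws, at least one abnormal is 9.6% v 5.9% at p = 2% and 41.0% v 27.1% at p = 10%. Counting Day 1 as a draw (6 v 4) gives 26.5% v 18.5% at p = 5%. The last column shows why the definition of *single* matters: read as exactly one, the direction reverses at ρ = 0.6 and above, and also for independent draws at p = 25% (39.6% v 42.2%).

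**Immunoglobulins, p = 5%, at least one low, A v B.** 9.8% v 14.3% at ρ = 0; 6.9% v 8.1% at ρ = 0.6; 5.5% v 5.7% at ρ = 0.9. These cases assume the chance of a low value does not change over time. If instead patients become low and stay low, any-low depends only on the last draw (Day 169 in A, Day 84 in B), and two low values depend on the penultimate draw (Day 85 v Day 56). Group A then has more time to qualify on both, and the tilt can run the other way.

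**Check of the remedy.** First immunization is on Day 85 in A and Day 1 in B. Days 112, 140 and 169 are 27, 55 and 84 days later; Days 28, 56 and 84 are 27, 55 and 83 days later. With three draws each, the no-effect rate at p = 5% is 14.3% v 14.3%.

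**The case against.** These are descriptive safety tables, no hypothesis is tested, and the SAP itself speaks only of summarizing by group. That is a fair limit on the importance of the point, but Protocol 6.5.2 does promise a comparison, and readers will make one.

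The size rests on assumed inputs. Where a patient's results hardly vary between visits, the gap nearly vanishes (6.0% v 5.7% at ρ = 0.9). This stands: the problem is material for sporadic abnormalities and negligible for persistent ones.

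Restricting the comparison to matched visits leaves the first 12 weeks after ocrelizumab without a comparator in that table. This also stands, and is why the full-ISP table should be kept.

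For immunoglobulins the objection is stronger. SAP 4.5 already plans the percentage below LLN at each timepoint, which does not depend on the number of draws. A reader might infer from the two v three draws that low immunoglobulin, an identified ocrelizumab risk, is understated in Group A, so that the two sets of tables err in opposite directions. The documents do not support that. Protocol 5.1.1.3 and 5.1.1.4 describe decreases that continue or are sustained, and under that pattern the later last draw in Group A can outweigh its smaller number of draws.

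**Conclusion.** The point holds for routine safety labs, including the AST/ALT percentage. With equal per-draw risk, the at-least-one percentage is higher in Group A at every correlation tried. At p = 5% the excess is 8.3 percentage points for independent draws (22.6 − 14.3), 1.5 at ρ = 0.6 and 0.3 at ρ = 0.9. With about 67 of 100 patients in Group A under 2:1 allocation, that is 0.083 × 67 = 5.6 patients down to 0.003 × 67 = 0.2. These sizes depend on assumed p and ρ and count scheduled draws only; unscheduled visits may add more. If *single* means exactly one, the direction can differ.

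For total Ig, IgA, IgG and IgM the pooled percentages are also not comparable, but no direction can be claimed. IgG subtypes are unaffected. This is a low-cost improvement to secondary, descriptive output; it does not touch the primary endpoint.

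**What to change.** In SAP 4.6.4.1:
- Define *single* and *replicated*.
- Base the A v B comparison of routine-lab abnormality and AST/ALT percentages on the visits 4, 8 and 12 weeks after first immunization: Days 112, 140 and 169 in Group A; Days 28, 56 and 84 in Group B. Use one value per patient per visit.
- Add the abnormality percentage at each visit.
- Keep the full-ISP table as a within-group description, with Group A Days 15 and 85 shown.

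In SAP 4.5:
- Rest the A v B immunoglobulin comparison on the planned percentage below LLN at each timepoint: Day 85 v Day 84 for equal time since baseline, and Day 169 v Day 84 for equal time since first immunization.
- State whether IgA is included, since the paragraph opens by naming only IgG, IgM and total Ig.
- Do not compare the pooled *replicated* percentage between groups.

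The cost is SAP wording and a visit filter in programming; no new samples or visits are needed. There are two downsides. Days 15 and 85 have no matched comparator in the restricted table. Matching on time since immunization also leaves Group A 12 weeks further from baseline, so abnormalities that build up with time in the study are not equalized by it.

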4.6.4.2 Anti-Drug Antibodies

The summaries described below for ADAs will be produced for both the ISP and for the OOE separately.

ADAs will be summarized descriptively. The baseline prevalence and postbaseline incidence of ADAs will be displayed. The number of patients with treatment-induced ADAs and the number of patients with treatment-enhanced ADAs will also be displayed.

A table will be presented that summarizes ocrelizumab serum concentrations ($\mu\text{g/mL}$) at timepoints when ADA samples were collected and analyzed (summary statistics: mean, median, SD, minimum, maximum, coefficient of variation [percentage], geometric mean, number, and percentage of samples with concentration $\leq 20 \mu\text{g/mL}$).

A listing by treatment group covering both ISP and OOE showing anti-ocrelizumab antibody data will be presented for patients with at least one ADA-sampled datum.

4.6.5 Vital Signs and Electrocardiogram

The summaries for vital sign parameters and ECG results will be presented separately within the ISP and OOE study periods.

The following vital signs parameters will be assessed:

- Systolic blood pressure

Ocrelizumab—F. Hoffmann-La Roche Ltd
31/Statistical Analysis Plan BN29739

- Diastolic blood pressure
- Pulse rate
- Respiratory rate
- Temperature
- Weight

For each vital signs parameter within each study period (ISP and OOE), absolute and change from baseline values will be summarized by treatment group at study visits that do not include an ocrelizumab infusion. For each vital signs parameter within each study period (ISP and OOE), absolute values and the value of the change from the pre-infusion baseline at that visit will be summarized by treatment group at each study visit that includes an ocrelizumab infusion (summary statistics: mean, median, SD, minimum, and maximum). At each visit at which vital signs parameters are assessed, summary statistics calculated will include mean, median, SD, minimum, and maximum. All vital signs data will be presented in a data listing by treatment group and covering all study periods.

ECG results will be summarized by treatment group within each study period (ISP and OOE) and will show the number and percentage of patients with normal, abnormal (not clinically significant), and abnormal (clinically significant) findings at baseline cross-tabulated with postbaseline ECG results in a shift table format. All ECG results will be presented in a data listing by treatment group and covering all study periods.

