Appendix 1 Schedule of Assessments: Tables A–C

TABLE A: SCHEDULE OF ASSESSMENTS FOR IMMUNIZATION STUDY PERIOD AND OPTIONAL OCRELIZUMAB TREATMENT PERIOD FOR GROUP A (A1 AND A2)

	Group A (A1 and A2)												
	Screening ¹	Immunization Study Period						OOE ^{2,3}			WD from Treatment	Unscheduled ⁴	Delayed Dosing ⁵
Study Day (unless noted) (Window)	-28 to -1	1 (BL) ¹	15 (± 2 d)	85 (± 4 d)	112 (± 4 d)	140 (± 4 d)	169 ² (± 4 d)	169 ² (± 4 d)	q22w (± 4 d) (-2 w prior to q24 w)	q24 w ³ (± 2 w)			
Week	-4 to -1	1	2	12	16	20	24	24	q22 w ³	q24 w ³			
↓=OCR infusion		↓	↓					↓		↓			
Informed consent ⁶	x												
Medical history, MS history, prior and concomitant treatments	x												
Eligibility review	x	x						x		x			
Physical and neurological exam	x	x	x		x	x	x		x	x	x	x	x
Vital signs ⁷	x	x	x	x	x	x	x		x	x	x	x	x
12-lead ECG ⁸	x	x	x				x	x		x	x		
Height	x												
Weight	x							x ⁹		x ⁹	x		
EDSS ¹⁰		x											

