Appendix 1 Schedule of Assessments: Table B

TABLE B: SCHEDULE OF ASSESSMENTS FOR IMMUNIZATION STUDY PERIOD AND OPTIONAL OCRELIZUMAB TREATMENT PERIOD

		Group B												
	Screening ¹	Immunization Study Period				OOE ^{2,3}						WD from Treatment ⁴	Unscheduled ⁴	Delayed Dosing ⁵
		1	28 (±4 d)	56 (±4 d)	84 ¹ (±4 d)	84 ¹ (±4 d)	98 (±2 d)	238 (±4 d)	252 (±2 d)	q22w (±4 d) (-2 w prior to q24 w)	q24 w ³ (±2 w)			
Study Day (Unless Noted) Window	-28 to -1	1	28 (±4 d)	56 (±4 d)	84 ¹ (±4 d)	84 ¹ (±4 d)	98 (±2 d)	238 (±4 d)	252 (±2 d)	q22w (±4 d) (-2 w prior to q24 w)	q24 w ³ (±2 w)			
Week	-4 to -1	—	4	8	12	12	14	34	36	q22 w ³	q24 w ³			
↓ = OCR infusion						↓	↓		↓		↓			
Informed consent ⁶	x													
Medical history, MS history, prior and concomitant treatments	x													
Eligibility review	x	x				x			x		x			
Physical and neurological examination	x	x				x	x		x		x	x	x	x
Vital signs ⁷	x	x	x	x	x	x	x		x		x	x	x	x
12-lead ECG ⁸	x	x				x	x		x		x	x		
Height	x													

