Appendix 1 Schedule of Assessments: Table B (cont.)

Group B														
	Screening ¹	Immunization Study Period				OOE ^{2,3}						WD from Treatment ⁴	Unscheduled ⁴	Delayed Dosing ⁵
Study Day (Unless Noted) Window	-28 to -1	1	28 (±4 d)	56 (±4 d)	84¹ (±4 d)	84¹ (±4 d)	98 (±2 d)	238 (±4 d)	252 (±2 d)	q22w (±4 d) (-2 w prior to q24 w)	q24 w³ (±2 w)			
Week	-4 to -1	—	4	8	12	12	14	34	36	q22 w³	q24 w³			
Weight ⁹	x					x			x		x	x		
EDSS ¹⁰		x												
MRI (once annually [±4 w]) ¹¹	x										x			
Adverse events	Only SAEs ¹²	x	x	x	x	x	x	x	x	x	x	x	x	x
Telephone interview						Every 4 weeks ¹³								
Concomitant treatments		x	x	x	x	x	x	x	x	x	x	x	x	x
Pregnancy test ¹⁴	x	x	x	x	x	x	x		x		x	x	x	x
ADA ¹⁵						x	x	x	x	x	x	x		
PK samples ¹⁶						x	x		x		x	x		
FSH ¹⁷	x													
Hepatitis screening ¹⁸	x													

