Appendix 1 Schedule of Assessments: Table B (cont.)

- 4 **Unscheduled Visit:** assessments performed at unscheduled (non-dosing) visits will depend on the clinical needs of the patient. Other tests/assessments may be done as appropriate.
- 5 A delayed dosing visit will be performed and recorded in the Delayed Dosing Visit eCRF form when dosing cannot be administered at the scheduled dosing visit. Other tests or assessments may be done as appropriate.
- 6 **Informed Consent** will be obtained in written form from all patients at screening in order to meet eligibility for the study.
- 7 **Vital signs** will be obtained while the patient is in the semi supine position (after 5 minutes), i.e., pulse rate, systolic, and diastolic blood pressure, respiration rate, and temperature. On OCR infusion visits, the vital signs should be taken within 45 minutes prior to the methylprednisolone infusion in all patients. In addition, vital signs should be obtained prior to the study drug infusion, then every 15 minutes (\pm 5 minutes) for the first hour; then every 30 minutes (\pm 10 minutes) until 1 hour after the end of the infusion. On immunization days, vital signs should be taken prior to immunization. On non-infusion/non-immunization days, the vital signs may be taken at any time during the visit.
- 8 **ECG (pre- and post-dose):** On infusion visits, ECG should be taken within 45 minutes prior to the methylprednisolone infusion in all patients, and within 60 minutes after completion of the OCR infusion. On non-infusion days, the ECG may be taken at any time during the visit.
- 9 Weight should be obtained prior to the OCR infusion.
- 10 The EDSS should be obtained at baseline (pre-dose). An EDSS should also be performed if PML is suspected.

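### SAP 4.6.5 yields no change from study baseline at any routine visit for weight (both groups) or for Group B's extension vital signs

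*SAP*

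**What the plan says.** SAP 4.6.5 lists systolic and diastolic pressure, pulse, respiratory rate, temperature and weight as the vital-sign parameters. It then sets two rules according to the type of visit:

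- Visits without an infusion: "absolute and change from baseline values will be summarized by treatment group at study visits that do not include an ocrelizumab infusion".
- Visits with an infusion: "absolute values and the value of the change from the pre-infusion baseline at that visit will be summarized by treatment group". No change from study baseline is mentioned here.

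The same section states: "The summaries for vital sign parameters and ECG results will be presented separately within the ISP and OOE study periods". It also promises a data listing of all vital signs over all study periods. It does not define study baseline.

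The visits come from Protocol Appendix 1, Table A (Group A) and Table B (Group B). Note 9 to both tables fixes when weight is measured at an infusion visit: "Weight should be obtained prior to the OCR infusion". No post-infusion weight is scheduled. Weight is not marked on Day 1 in either table, so screening is the only pre-treatment value.

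**The concern.** The SAP rule works only if each parameter is measured at some routine visits without an infusion. If it is not, the change-from-baseline table has no routine data for that parameter, and the within-visit change stands in its place. For blood pressure or pulse, the within-visit change describes infusion reactions, which is a sensible purpose. For weight measured once per visit it describes nothing.

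What is at stake is a by-group summary of within-patient change in weight and, in Group B's extension, in blood pressure, pulse, respiratory rate and temperature. The few changes that the rule would produce come from patients who withdrew or needed an extra visit. A reader could mistake them for the treated group as a whole. No immunology endpoint is affected.

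**Working it through.** No figure in the plan needs reproducing. The check reads the weight, vital-sign and ocrelizumab-infusion rows of Tables A and B column by column and compares them with the two SAP rules.

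**Infusion columns**

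- Group A: Days 1 and 15, Day 169 (extension column), q24w, delayed dosing.
- Group B: Day 84 (extension column), Days 98 and 252, q24w, delayed dosing.
- No infusion in either group: q22w, withdrawal, unscheduled. In Group B also Day 238.

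**Where the readings fall**

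| Parameter | Routine visits at which it is taken | With infusion | Without infusion | Other visits without infusion |
|---|---|---|---|---|
| Weight after screening, Group A | Day 169 extension, q24w | 2 of 2 | 0 of 2 | Withdrawal |
| Weight after screening, Group B | Day 84 extension, Day 252, q24w | 3 of 3 | 0 of 3 | Withdrawal |
| Extension vital signs, Group B | Days 84, 98, 252, q24w | 4 of 4 | 0 of 4 | Withdrawal, unscheduled |
| Extension vital signs, Group A (as the table reads) | q22w, q24w | 1 of 2 | 1 of 2 (q22w) | Withdrawal, unscheduled |

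**Applying the rules**

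1. Weight. Every routine post-screening weight falls under the infusion-visit rule, so none yields a change from study baseline. The change that the rule does ask for is a later reading minus the pre-infusion reading at the same visit. Only the pre-infusion reading exists. The result is undefined, or zero if that reading is subtracted from itself.
2. Group B extension vital signs. All four routine visit types fall under the infusion-visit rule. The two routine extension visits without an infusion, Day 238 and q22w, have no vital signs marked (0 of 2). No routine visit yields a change from study baseline.
3. Group A extension vital signs. The q22w visit is marked and has no infusion, so it does yield one. The extension table would hold routine data for Group A and none for Group B.
4. What is left. Withdrawal visits (weight and vital signs) and unscheduled visits (vital signs) have no infusion and would give a change from study baseline for the patients who attend them. Delayed dosing visits include an infusion and would not.

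**Comparison within the SAP**

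SAP 4.6.4.1 summarizes laboratory change from baseline at every visit, with no exception for infusion visits. It defines baseline as the last value before first ocrelizumab in Group A and before first immunization in Group B. SAP 4.6.5 has neither feature.

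**The case against.** Several points on the other side stand.

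- A reader might infer that these changes are never produced, or that the readings are taken only at infusion visits. The schedules do not support that. Withdrawal visits give a change for weight and vital signs, and unscheduled visits give one for vital signs. The defensible statement is that no routine visit gives one.
- A reader might infer that drift over time cannot be seen. That is too strong. Absolute values are summarized at infusion visits too, by group, with mean, median, SD and range, and all vital signs are listed. What is missing is the paired change. Successive means over a changing set of patients are only a partial substitute.
- A reader might infer that patients who start the extension on Day 169 (Group A) or Day 84 (Group B) lose their last immunization-period change, so that end-of-period change describes only those who declined ocrelizumab. The documents point the other way. Each of these days has a separate immunization-period column without an infusion. Note 2 to both tables requires those assessments for all patients, and SAP 4.6.5 splits its summaries by period.
- The contrast between the groups depends on one row of Table A. That row is blank for vital signs at the Day 169 extension infusion, although note 7 calls for vital signs at infusion visits, and it is marked at q22w. This could be a shifted cell in the extracted table. The physical-examination row of Table A shows the same pattern, which makes an isolated slip less likely but does not settle it. If the mark belongs at Day 169, Group A also has no routine non-infusion vital-sign visit in the extension. The groups would then be equal, and the gap would be wider.
- Protocol 3.4.4 ties vital signs to monitoring infusion reactions, and SAP 2.2.4 describes them as taken before, during and after infusion. The within-visit change serves that purpose. Weight appears in neither list of safety outcomes. This limits the importance of the gap. It does not explain why SAP 4.6.5 plans a change from baseline and a within-visit change for weight under rules that give almost none.
- This SAP reports data at the cutoff for the Immunization Study Period (SAP 2.4), so the extension tables will hold only what is available by then.

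**Conclusion.** The concern holds as a minor gap in descriptive, untested safety tables. Under SAP 4.6.5, change from study baseline is available at 0 of 2 routine post-screening weight visit types in Group A, 0 of 3 in Group B, and 0 of 4 routine vital-sign visit types in Group B's extension. The within-visit change for weight is empty or zero by construction. The only changes from study baseline would come from withdrawal and unscheduled visits, which describe a selected subset.

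The conclusions on weight and on Group B rest on the schedule rows as extracted and on the literal wording of the two SAP rules. The unequal handling of the groups rests in addition on Group A's q22w mark being genuine. Primary and secondary immunology results are untouched, and nothing has to be collected that is not already collected.

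**What to change.** Replace the two visit-type rules in SAP 4.6.5 with wording such as:

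> At every visit, absolute value and change from study baseline are summarized, using the reading taken before methylprednisolone at infusion visits and the visit reading at other visits. Study baseline is the last value before first ocrelizumab (Group A) or first immunization (Group B), which for weight is the screening value. At infusion visits the within-visit change from the pre-infusion reading is summarized in addition, except for weight.

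This brings vital signs into line with the laboratory rule in SAP 4.6.4.1 and gives both groups the same summary whatever Table A's q22w cell should show. The cost is a few lines of SAP text and one more column in existing tables. The visit schedule does not change.
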